### 7.3. Justification of Sample Size

(Sample size calculations were prepared by [name]. of the HCI Biostatistics Resource)

Our justification of sample size is based on the data from Chen et al and Schwarzenberg et al. (Chen et al., 2007, Schwarzenberg et al., 2012) in which a more than 25% reduction in tumor [F]FLT uptake as measured by standardized uptake value was defined as a metabolic response. In this study there were nine responders (47%) and 10 non-responders (53%). Responders survived three times as long as non-responders (10.8 v 3.4 months;  $P = .003$ ), and tended to have a prolonged progression-free survival ( $P = .061$ ). Both early and later [F]FLT -PET responses were more significant predictors of overall survival (1 to 2 weeks,  $P = .006$ ; 6 weeks,  $P = .002$ ), compared with the MRI responses ( $P = .060$  for both 6-week and best responses). A potential limitation of this study was the use of standardized uptake value rather than full kinetic analysis in brain tumors (Peck et al., 2015). We will use full kinetic modelling and hopefully provide even more robust response data for [F]FLT. Since there are no human studies utilizing [F]Fluciclovine to measure response we have extrapolated from the available human xenograft rat glioma study of Ono et al. (2015b) utilizing anti-C-FACBC with U87 and U87R (TMZ-resistant subculture) cells which were inoculated into the right and left basal ganglia. In autoradiographic experiments the DAR of anti-C-FACBC was significantly higher in tumors than in non-involved cortices. C-FACBC accumulation was lower after single-agent treatment and lower still after combination therapy. Treatment with temozolomide

alone significantly decreased the T/NT for the DAR of U87 tumors, whereas the T/NT ratios for those of U87R tumors remained unchanged. Temozolomide and interferon- $\beta$  combination treatment significantly decreased anti-C-FACBC uptake in both U87R and U87 tumors. Addition of bevacizumab to the temozolomide and interferon- $\beta$  combination further decreased anti-C-FACBC uptake in both tumor types.

With an initial sample size of 30, we estimate that approximately 75% of the subjects (N = 22) will have both a [F]Fluciclovine-PET and [F]FLT-PET after completion of initial chemoradiotherapy. Our justification of sample size is based on data on the prediction of OS using PET reported in Chen et al. (Chen et al., 2007). In this study more than 25% reduction in tumor [F]FLT uptake as measured by standardized uptake value was defined as a metabolic response. In this study there were nine responders (47%) and 10 non-responders (53%). Responders survived three times as long as non-responders (10.8 v 3.4 months;  $P = .003$ ), and tended to have a prolonged progression-free survival ( $P = .061$ ). Both early and later [F]FLT - PET responses were more significant predictors of overall survival (1 to 2 weeks,  $P = .006$ ; 6 weeks,  $P = .002$ ), compared with the MRI responses ( $P = .060$  for both 6-week and best responses). In univariate and multivariate Cox regression analysis, lack of FLT reduction at 6 weeks was the best predictor of reduced OS, with adjusted hazard ratio = 4.955 ( $p = 0.02$ ). Assuming 50% of subjects are metabolic responders, median survival of 3.4 months in non-responders and two years of follow up, a sample size of N = 22 subjects with follow up PET scans will provide 85% power to detect a hazard ratio of 4.9 using a two-sided logrank test at the 0.0125 significance level.

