## 2. BACKGROUND

### 2.1. Malignant Brain Tumors

Despite significant advances in the understanding of brain tumor biology and genetics as well as improvements in surgical techniques, radiotherapy administration, and chemotherapy methods; most primary brain tumors remain incurable. Most primary brain tumors are highly infiltrative neoplasms, and are therefore unlikely to be cured by local treatments such as surgery, focal radiotherapy, radiosurgery, or brachytherapy.

The clinical presentation of a brain tumor is highly dependent on its location within the nervous system; but includes signs/symptoms that relate directly to compression and/or infiltration of specific functional areas of brain parenchyma, increased intracranial pressure, hydrocephalus, cerebral edema, and/or vascular complications from the tumor. The most common symptoms include headaches, cognitive deficits, nausea/vomiting, seizures, balance disturbances, and focal neurologic deficits. Once clinically suspected of having such a lesion, a patient usually undergoes an imaging procedure, typically a computed tomography (CT) scan or a magnetic resonance (MR) scan. Neurosurgical intervention, in the form of either a brain biopsy or craniotomy with resection, is the next step to obtain a tissue diagnosis and, if warranted, to decrease the tumor mass.

There are approximately 16,900 new cases of primary CNS tumors diagnosed in the United States each year. Numerous studies have documented an increase in the incidence of these tumors in the last decades (Sanson-Fisher et al., 2000). About 50% of these lesions are supratentorial high-grade gliomas. Anaplastic astrocytoma (AA) (WHO Grade III) and glioblastoma (GBM) (WHO Grade IV) are the most common glial primary brain tumors with at least 80% of malignant gliomas being GBMs (Brock et al., 1998, Ichimura et al., 1998). Patients with newly diagnosed malignant gliomas are usually treated with biopsy or surgical resection followed by radiation therapy and/or chemotherapy; depending on their functional status. Despite these interventions, the median survivals for newly diagnosed GBM and AA are 50 and 150 weeks, respectively. Chemotherapy has been shown to increase the proportion of long-term survivors from less than 5% to between 15-20 % (Treat et al., 2012). Once a patient has failed initial therapy, salvage therapy is difficult and most patients die of tumor progression within 4-12 months (Group, 2002).

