The data from multiple PET biomarkers combined with histologic and clinical data will enable identification and development of PET biomarker profiles which correlate with (and might be predictive of) tumor aggressiveness and clinical outcomes. The three imaging time point assessments serve multiple uses in this initial exploratory study. If baseline imaging can predict tumor aggressiveness and clinical outcomes, such imaging may potentially be used to guide selection of conventional, aggressive, or investigational therapies. The second time point, within 1-4 weeks after 6wks of chemoradiotherapy, will provide a measurement of tumor response that may potentially differentiate tumors that will progress rapidly from those that will not (changes in imaging biomarkers between exams 1 and 2 will likely be important for this determination). Finally, the multi-tracer array at the time of treatment effect (pseudoprogression) versus true recurrence/progression may yield new insights into the physiology and biology of these tumors, and multi-tracer imaging may help to differentiate recurrence from radiation necrosis/treatment effect (pseudoprogression). We believe the complementary value of the two tracers in conjunction has much greater potential for meeting these goals than any one tracer alone. For example, tumors with high proliferation ([F]FLT) and/or growth ([F]Fluciclovine) may respond best to anti-EGFR-directed agents or conventional cytotoxic chemotherapies. Of specific interest, is there a multi-tracer PET signature that distinguishes between treatment effect (pseudoprogression) and true progression/recurrence that will have important clinical utility? These questions will be studied in detail, developing formal hypotheses that will be tested in future phase II/III clinical trials.

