### 5.5.2. Multi-Tracer PET Exams

Multi-tracer PET exams of [F]FLT and [F]Fluciclovine will be acquired in each patient at up to three time points: (1) prior to any tumor-directed therapy, either prior to surgery or after surgery providing a complete surgical resection was not performed and confirmed by a post-operative contrast MRI scan where residual tumor  $\geq 1.0$  cm in diameter was present and prior to any tumor-directed therapy; (2) within 1-4 weeks after the conclusions of the initial (~6-8 weeks) chemoradiotherapy; and (3) patients with MRI-documented possible recurrence/progression versus treatment effect (pseudoprogression) within 6 months from the time of completion of chemoradiation. The abnormality must be  $\geq 1.0$  cm in diameter by contrast MRI or CT or show changes on non-enhancing MRI sequences (T2 or FLAIR).

Patients who were originally not enrolled to study baseline and conclusion of therapy imaging will be eligible to participate at the time of MRI-documented possible recurrence/progression versus treatment effect (pseudoprogression) within 6 months from the time of completion of chemoradiation. The abnormality must be  $\geq 1.0$  cm in diameter by contrast MRI or CT or show changes on non-enhancing MRI sequences (T2 or FLAIR).

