### 6.2.2. [F]Fluciclovine Semi-Quantitative Assessment

Semi-quantitative assessment of [F]Fluciclovine uptake will be performed by calculating  $SUV_{max}$  and  $SUV_{mean}$  in the same manner as for [F]FLT described earlier. SUVs will be calculated for summed static images from 70 minutes post injection. The change in SUVs for pre-treatment (baseline) and post-treatment images will be computed and correlated with available histologic and clinical data.

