#### Primary Endpoint

The primary endpoint of the study is that a 25% reduction in  $SUV_{max}$  or  $SUV_{mean}$  for each of the PET imaging tracers will be predictive of increased overall survival. These endpoints will be analyzed by

Kaplan-Meier analysis and logrank tests. Cox proportional hazards regression will also be used to estimate hazard ratios. Each analysis will be performed at the two sided 0.0125 significance level to adjust for four comparisons.

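### Does the N = 22 behind the 85% power fail to count patients with both a baseline and a post-therapy scan, and leave too little room for Group B?

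*Combined protocol and SAP*

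**What the plan says.** Section 7.3 starts from 30 enrolled patients and expects "With an initial sample size of 30, we estimate that approximately 75% of the subjects (N = 22) will have both a" fluciclovine and an FLT scan once initial chemoradiotherapy is complete. It concludes that "a sample size of N = 22 subjects with follow up PET scans will provide 85% power" for a hazard ratio of 4.9, with a two-sided logrank test at 0.0125, half the patients metabolic responders, a median of 3.4 months in non-responders and two years of follow-up.

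Section 7.2 opens the primary analysis with "The primary endpoint of the study is that a 25% reduction in" SUVmax or SUVmean, for each tracer, as a predictor of longer overall survival. That paragraph does not name the two scans or an analysis set.

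Other sections supply the pair. Section 6.2.2, with matching text for FLT in section 6.1.2, says "The change in SUVs for pre-treatment (baseline) and post-treatment images will be computed and correlated with available histologic and clinical data". Section 4.3.1, after Table 3, says of the second time point that "changes in imaging biomarkers between exams 1 and 2 will likely be important for this determination". Section 5.5.2 places that scan "within 1-4 weeks after the conclusions of the initial (~6-8 weeks) chemoradiotherapy".

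Group B enrols only at suspected pseudoprogression, within 6 months of completing chemoradiation (sections 1.1 and 5.5.2). It shares the 30 places with Group A (section 5.1), and no section gives the split.

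**The concern.** Read literally, section 7.3 counts patients by their scans after chemoradiotherapy. Group B patients also have both tracers after chemoradiation, so the wording does not exclude them, yet they have no baseline and no change score. With 20 patients in Group A and 10 in Group B, for example, roughly 27 to 28 people could have scans after chemoradiation while only 17 to 18 had a usable pair (arithmetic below).

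The 8 places outside the 22 are also not allocated. If a reader took all 8 as free for Group B, every one of the 22 Group A patients would have to reach the second scan, and in high-grade glioma some would be expected to die first. The stake would be an overstated number of evaluable patients, and so overstated power, for the four primary tests.

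**Working it through.** **1. The plan's power.** Inputs from section 7.3: 11 patients per group, non-responder median 3.4 months, HR 4.9 (responder median 3.4 × 4.9 = 16.66 months), two-sided alpha 0.0125. Section 5.1 gives 8 to 10 patients a year, so 30 patients take 36 to 45 months. Assumptions: exponential survival, uniform accrual over a = 36 months, then f = 24 months' follow-up.

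P(event) = 1 − exp(−λf) × [1 − exp(−λa)]/(λa)

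- Non-responders, λ = ln2/3.4: 0.999
- Responders, λ = ln2/16.66: 0.809
- Events: 11 × (0.999 + 0.809) = 19.9

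Schoenfeld power = Φ(√(19.9/4) × ln 4.9 − 2.498) = Φ(1.046) = 85.2%. With 45 months' accrual it is 85.8%. The stated 85% reproduces.

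**2. The count of 22.** 0.75 × 30 = 22.5, taken as 22. The percentage is over all 30, so the remaining 8 cover Group B and Group A losses together. The estimate holds if those total 8 or fewer.

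**3. Who can be analysed.**

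| Place | What it fixes |
|---|---|
| 7.2, primary endpoint | A reduction, so two scans |
| 7.3 | Half are responders, which is a classification by change |
| 6.1.2 and 6.2.2 | SUV change is pre-treatment against post-treatment |
| 7.2, secondary objectives | Kinetic markers are compared from baseline to post therapy |
| Appendices C and D | Visit 2 is labelled follow-up; visit 3 is labelled pseudoprogression |

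Section 7.3 describes its 22 as having follow-up scans after initial chemoradiotherapy, which matches visit 2. A Group B patient has no value to enter.

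**4. Group A patients needed for 22 expected pairs.** Section 2.1 states that "the median survivals for newly diagnosed GBM and AA are 50 and 150 weeks, respectively", "with at least 80% of malignant gliomas being GBMs". Section 5.5.2 puts the second scan 6 + 1 = 7 to 8 + 4 = 12 weeks after chemoradiotherapy starts. Assumptions: exponential survival, baseline scan at the start of chemoradiotherapy, death the only loss.

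S(w) = 0.8 × 2^(−w/50) + 0.2 × 2^(−w/150)

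- 7 weeks: 0.8 × 0.9075 + 0.2 × 0.9682 = 0.920; 22/0.920 = 23.9, so 24
- 12 weeks: 0.8 × 0.8467 + 0.2 × 0.9461 = 0.867; 22/0.867 = 25.4, so 26
- All GBM: 22/0.9075 = 24.2, so 25; 22/0.8467 = 26.0, so 26

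That leaves 30 − 24 = 6 to 30 − 26 = 4 places for Group B. With 20 in Group A, the expected pairs are 20 × 0.920 = 18.4 to 20 × 0.867 = 17.3.

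**5. Sensitivity.** A further 4 weeks before chemoradiotherapy (16 weeks in all) gives 27 to 28. An extra 10% loss for reasons other than death gives 27 to 29. All of these still fit within 30.

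**The case for a change.** The best case for a change is that membership of the four primary tests should be written down rather than inferred. The kinetic secondary objectives in section 7.2 name the baseline-to-post-therapy comparison, and the primary paragraph beside them does not. The 24 to 26 is also optimistic in places: a baseline before surgery, enrolment before pathology, or refusals would raise it. If pairs fell short, power would drop. On the Schoenfeld basis above it is 81% at 20 pairs, 76% at 18 and 70% at 16.

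The omission is real, and so is the direction of the loss. Two things limit it.

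- No section allots all 8 places to Group B or gives any split, so a shortfall is hypothetical.
- The reduced powers are not firm enough to replace the plan's figure. They depend on the assumed 36-month accrual and on the formula. With exactly 24 months' follow-up per patient, Schoenfeld gives 80.5% at 22, 76% at 20 and 64% at 16. A simulated logrank test with the longer follow-up gives about 77%, 72% and 57%. They also use a 3.4-month non-responder median, while the attrition step uses 50 and 150 weeks, so the two steps rest on different survival models.

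**Conclusion.** No change is needed. The plan omits a sentence naming the scan pair and gives no split of the 30 places, but the endpoint's own definition restricts the primary tests to patients with a baseline and a post-therapy scan. An analyst following the plan as written arrives at that set. The count of 22 from 30 is coherent if Group B and Group A losses together total 8 or fewer. The section 2.1 survival figures allow this, at about 24 to 26 Group A patients and 4 to 6 in Group B.

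That range is an illustration, not a bound: it assumes exponential survival, loss by death only and a baseline at the start of chemoradiotherapy. The 85% reproduces when accrual time is added to the two years of follow-up. For a study that calls itself exploratory, writing down the inferable definition would be tidy but would not alter who is analysed, the tests or the stated power.

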A number of quantitative and semi-quantitative imaging biomarkers for each tracer will be computed at each imaging time point, and the change in each biomarker between time-points will also be computed. These data will be compared with changes in tracer uptake before and after therapy and used to determine the semi-quantitative change in [F]FLT and [F]Fluciclovine uptake which is consistent with response based on standard brain tumor response. In addition the imaging biomarkers will be used to determine if they are predictive endpoints (survival, time to progression), and with tumor biologic information (histology, WHO grade, vascularity, MIB-1, VEGF, EGFR, p53, IDH status) in cases when tumor tissue becomes available from standard care. These data will provide pilot information regarding the potential value of concurrent multiple PET biomarkers for predicting tumor behavior prior to the start of therapy, for improved prognostication, for more efficient and effective tumor surveillance, and/or for more appropriate assignment of patients to conventional, aggressive, or investigational therapies early in their clinical courses.

All patients will receive standard tumor-directed therapy and will be monitored with conventional imaging according to standard of care, which may include MRI and FDG-PET as described earlier. The [F]FLT or

[F]Fluciclovine PET research scans will *not* affect clinical decisions. A database of demographic, clinical, and molecular biologic information for each patient will be created. Tissue samples, when available from routine care, will undergo detailed histopathologic evaluations, with results prospectively and systematically recorded. All patients will be followed until the end of the trial (at least 12 months post last imaging assessment) for important clinical endpoints as listed in Table 3.

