## 5.2. Inclusion Criteria

- Two adult patient groups will be eligible for inclusion in this study:
  - Group A: Patients where there is compelling evidence, based on the MRI and/or CT imaging, that a high-grade primary brain tumor is present. Pathologic confirmation will occur with biopsy or surgery.  
Patients whose tumor is felt to be inoperable and a biopsy is performed but no surgery.  
Patients with a newly diagnosed primary malignant brain tumor (WHO Grade III or IV) who will be receiving chemoradiation and who either did not undergo surgical resection or underwent incomplete resection with residual tumor  $\geq 1.0$  cm in greatest diameter by contrast MRI postoperatively.
  - Group B: Patients with pathologically proven malignant brain tumor (WHO Grade III or IV glial-based tumors) who have undergone chemoradiation and have MRI-documented possible recurrence/progression versus treatment effect (pseudoprogression) within 6 months from the time of completion of chemoradiation.
- Patients must be 18 years or older for inclusion in this study. There is little experience with the safety of [F]FLT or [F]Fluciclovine in children, and the risks associated with radiation exposure may be increased for children under 18 years old as well.
- Patients must document their willingness to be followed for up to 24 months after recruitment by signing informed consent documenting their agreement to have clinical endpoints and the results of histopathologic tissue analysis (when tissue becomes available from routine care) entered into a research database.
- All patients, or their legal guardians, must sign a written informed consent and HIPAA authorization in accordance with institutional guidelines.
- Determination of pregnancy status: Female patients who are not postmenopausal or surgically sterile will undergo a serum pregnancy test prior to each set of [F]FLT and [F]Fluciclovine PET scans. A negative test will be necessary for such patients to undergo research PET imaging.

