## APPENDIX A: Eligibility Check List

**Patient Name:** \_\_\_\_\_ **MRN:** \_\_\_\_\_

**Person Confirming Eligibility:** \_\_\_\_\_ **Date:** \_\_\_\_\_

\_\_\_\_\_ (Yes/No) Patient is  $\geq$  18 years old.

\_\_\_\_\_ (Yes/No) Group A. Either patients where there is compelling evidence, based on the MRI and/or CT imaging, that a high-grade primary brain tumor is present. Pathologic confirmation will occur with biopsy or surgery. OR patients whose tumor is felt to be inoperable and a biopsy is performed but no surgery. OR patients with a newly diagnosed primary malignant brain tumor (WHO Grade III or IV) who will be receiving chemoradiation and who either did not undergo surgical resection or underwent incomplete resection with residual tumor  $\geq$  1.0 cm in greatest diameter by contrast MRI postoperatively.

\_\_\_\_\_ (Yes/No) Group B. Patients with pathologically proven malignant brain tumor (WHO Grade III or IV glial based tumors) who have undergone chemoradiation and have MRI-documented (contrast enhancing mass  $\geq$  1.0 cm in greatest diameter) possible recurrence/progression versus treatment effect (pseudoprogession) within 6 months from the time of completion of chemoradiation.

\_\_\_\_\_ (Yes/No) Patient is willing to have their clinical records reviewed for at least 24 months after enrollment.

\_\_\_\_\_ (Yes/No) Patient, or their legal guardians, have signed a written informed consent and HIPAA authorization in accordance with institutional guidelines.

\_\_\_\_\_ (Yes/No) If patient is female, she must be postmenopausal for a minimum of one year, surgically sterile, or is willing to undergo a serum pregnancy test prior to each imaging session.

\_\_\_\_\_ (Yes/No) Patient is not lactating.

\_\_\_\_\_ (Yes/No) Pre- [F]Fluciclovine and [F]FLT PET laboratory tests not greater than 4.0 $\times$  the upper or lower values in the normal range: liver enzymes (AST, ALT, ALK), bilirubin (total), serum electrolytes, CBC with platelets, prothrombin time, partial thromboplastin time, BUN, and creatinine. For those patients receiving coumadin or another anticoagulant the upper limit for prothrombin time or partial thromboplastin time must not exceed 6 times the upper limit of the normal range.

\_\_\_\_\_ (Yes/No) Patient does not have allergic or hypersensitivity reactions to previously administered radiopharmaceuticals.

\_\_\_\_\_ (Yes/No) Patient does not require monitored anesthesia for PET/CT imaging.

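### The 85% power in section 7.3 rests on an undefined two years of follow-up that conflicts with the plan's other follow-up rules, and should be restated under one rule

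*Combined protocol and SAP*

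**What the plan says.** Overall survival by metabolic response is the primary endpoint, tested for two tracers and two SUV measures: "Each analysis will be performed at the two sided 0.0125 significance level to adjust for four comparisons" (section 7.2, Primary Endpoint).

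Section 7.3 sets out the power. The inputs are "Assuming 50% of subjects are metabolic responders", "median survival of 3.4 months in non-responders and two years of follow up" and "a sample size of N = 22 subjects with follow up PET scans", and the result is that this "will provide 85% power to detect a hazard ratio of 4.9 using a two-sided logrank test at the 0.0125 significance level". It gives neither the starting point of the two years nor an accrual period.

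Three other places state how long patients are followed:

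- Section 4.3, under Secondary Exploratory Objectives: "All patients will be followed until the end of the trial (at least 12 months post last imaging assessment". This is a floor, with follow-up continuing to the end of the trial.
- Section 5.2: patients document "willingness to be followed for up to 24 months after recruitment". As worded, this is a ceiling.
- Appendix A: patients agree to record review for "at least 24 months after enrollment". This is a floor.

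Sections 5.2 and Appendix A describe the same willingness criterion with opposite bounds. Section 5.1 gives accrual as eight to ten patients a year, to 30.

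**The concern.** Log-rank power depends on the number of deaths, so the length of follow-up is an input to the 85%. The power statement uses two years, but no operational section clearly delivers two years from the scan that defines response. Section 5.5.2 puts that scan 1 to 4 weeks after about 6 to 8 weeks of chemoradiotherapy, so 24 months counted from recruitment is less than two years from the scan.

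The deaths at risk of being missed are mainly those of responders. Under the plan's assumptions, 91% of non-responders have died by 12 months and 99% by 24 months; for responders the figures are 39% and 63%. At stake is whether the stated power describes the trial that will be run, and whether sites know when survival follow-up may stop.

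**Working it through.** **Inputs.** N = 22, split 11 and 11; non-responder median 3.4 months; hazard ratio 4.9; two-sided alpha 0.05/4 = 0.0125 (sections 7.2 and 7.3). Accrual is 30/10 = 3 years to 30/8 = 3.75 years, or 36 to 45 months (section 5.1).

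**Assumptions made here.** Exponential survival, uniform accrual, survival counted from the post-therapy scan, and no loss to follow-up.

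**Hazards.** Non-responders: ln 2/3.4 = 0.2039 per month. Responders: 0.2039/4.9 = 0.0416 per month, a median of 3.4 × 4.9 = 16.66 months.

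**Probability of death.** With fixed follow-up F it is 1 − exp(−λF). With accrual A and then a minimum of F months it is 1 − [exp(−λF) − exp(−λ(F + A))]/(λA).

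**Schoenfeld power.** Φ(√d × ln(4.9)/2 − 2.498), where d is the expected number of deaths and ln(4.9)/2 = 0.7946.

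**The plan's figure.** Take 36 months of accrual and then 24 months: d = 19.89, √19.89 × 0.7946 = 3.544, 3.544 − 2.498 = 1.046, and Φ = 85.2%. With 45 months of accrual, d = 20.16 and power is 85.8%. So the 85% is recovered, but the first patients are followed for 36 + 24 = 60 to 45 + 24 = 69 months.

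**Exactly 24 months each.** d = 11 × (0.9925 + 0.6316) = 17.86, √17.86 × 0.7946 = 3.358, 3.358 − 2.498 = 0.860, and Φ = 80.5%.

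**All readings**, with a simulated log-rank test beside the formula (at least 20,000 trials, so a simulation standard error of about √(0.77 × 0.23/20,000) = 0.3 points):

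| Reading | Deaths | Schoenfeld | Simulated |
|---|---|---|---|
| 36-month accrual, then 24 months | 19.89 | 85.2% | 77.0% |
| 45-month accrual, then 24 months | 20.16 | 85.8% | 77.2% |
| Exactly 24 months each | 17.86 | 80.5% | 76.6% |
| 36-month accrual, then 12 months | 18.41 | 81.9% | 75.3% |
| 45-month accrual, then 12 months | 18.88 | 83.0% | 75.9% |
| Section 5.2 limit: 20 to 21.5 months after scan 2 | 17.03 to 17.37 | 78.3 to 79.2% | 75.8% at 20.5 months |
| Everyone censored at 12 months (lower bound, not prescribed) | 14.37 | 69.7% | 67.1% |

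The section 5.2 row assumes that scan 2 falls 2.5 to 4 months after recruitment, which leaves 24 − 4 = 20 to 24 − 2.5 = 21.5 months.

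**Two effects are separate.** Going from a 24-month to a 12-month minimum costs 85.2 − 81.9 = 3.3 or 85.8 − 83.0 = 2.8 points by formula, and between 1 and 2 points by simulation. Going from formula to simulation costs about 8 points (85.2 v 77.0) with follow-up held fixed. The formula treats the risk set as balanced throughout; with a hazard ratio of 4.9 the non-responders die out early and it becomes unbalanced. Longer follow-up does not close that gap: exactly 36 months each gives 77.4% simulated.

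**The case against.** A reader might infer that the plan guarantees only 12 months, so that power falls to about 67 to 70%. The documents do not support that. Section 4.3 follows everyone to the end of the trial, and 12 months is a floor that binds only for the last patients. With 36 to 45 months of accrual, early patients have up to 48 to 57 months. The floor also runs from the last imaging, which for some patients is the third scan and so later than scan 2.

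A reader might also infer that consent caps follow-up at 24 months. Section 5.2 is a willingness criterion, Appendix A words the same criterion as a minimum, and section 4.3 sets no maximum. The consent pages are not in the public copy. This is a conflict of wording, not an established cap.

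Larger losses could be shown by replacing the 3.4-month median with the 50 weeks that section 2.1 gives for newly diagnosed glioblastoma. That would be a criticism of the survival assumption, a different point from follow-up length.

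Finally, 75% of 30 is 22.5. With 23 patients, the 12-month minimum under staggered accrual gives 83.9 to 84.9% by Schoenfeld. The plan states 22, however, and exactly 24 months each still gives only 82.5% with 23.

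These replies stand as limits on the size of the shortfall. They do not reconcile the four statements or supply the missing time origin.

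**Conclusion.** The follow-up statements conflict, and the 85% depends on a reading that section 7.3 does not state, section 4.3 does not require and section 5.2, as worded, does not allow. Of the readings tried at N = 22 and two-sided 0.0125, only 24 months beyond a 36- to 45-month accrual gives 85%, and then only by the Schoenfeld formula. The plan's own rules give 82 to 83% (75 to 76% simulated) with the 12-month minimum and staggered accrual, and 78 to 79% (about 76% simulated) under the section 5.2 limit.

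It would be too strong to say that short follow-up is why 85% is missed. Exactly 24 months each already gives 80.5%, or 77% simulated. The 12-month minimum costs about 1 to 3 points under planned accrual, and about 10 only if everyone were censored at 12 months. These results rest on the assumptions listed above and on the plan's 3.4-month median.

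**What to change.** Reconcile sections 4.3, 5.2 and 7.3 and Appendix A into one survival follow-up rule counted from the post-therapy scan. One workable form is vital status by record review until death or the end of the trial, with a minimum of 24 months after that scan and no 24-month maximum. In section 7.3, state the time origin, the accrual period and the method of calculation, and replace the 85% with the power under the chosen rule. With the 24-month minimum that is about 77% by simulated log-rank test. If the 12-month minimum is kept, restate the power for that instead, at 75 to 76% by simulation.

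The cost is longer record review, a change to the consent and checklist wording, a later database lock for the last patients, and a less favourable stated power. No further scans are needed.
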